9.1.6.3. Assessment of Puberty

CCI [REDACTED]

The date of onset of menstruation will also be collected.

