To evaluate the effect of treatment with mirikizumab on height velocity at Weeks 12, 24, and 52	Observed height velocity by gender and age group will be calculated at baseline, Week 12, Week 24, and Week 52
To evaluate the effect of treatment with mirikizumab on weight throughout the trial	Change from baseline in weight (kg) at all study visits by gender and age group
To evaluate the effect of treatment with mirikizumab on pubertal development throughout the trial in appropriate patient groups	Hormone levels and/or other related clinical measures will be evaluated
To evaluate the effect of treatment with mirikizumab on improving	Change from baseline in 7-day average of Abdominal Pain (in past 24 hours) NRS score at Week 12 and Week 52
patient-reported outcome endpoints at Week 12 and Week 52	The proportion of patients with a NRS pain score ≥3 at baseline who achieve an improvement of ≥30% from baseline in 7-day average abdominal pain NRS score at Week 12 and Week 52
To evaluate histologic-endoscopic mucosal remission following	Proportion of patients with histologic-endoscopic mucosal remission at Week 12
mirikizumab treatment at Week 12 or Week 52	Proportion of patients with histologic-endoscopic mucosal remission at Week 52
	Histologic-endoscopic mucosal remission is defined as achieving both histologic remission and endoscopic remission. Histologic remission is defined in Section 6.10.1.
To evaluate the development of antimirikizumab antibodies and their effect	Proportion of patients who have treatment-emergent anti-drug antibodies (TEADA)
CCI	CCI

Abbreviations: NRS = numeric rating scale; PK = pharmacokinetic; PUCAI = Pediatric Ulcerative Colitis Activity Index.

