6.1.2. Baseline Definition

The baseline for variables collected as part of the old diary (including the SF and rectal bleeding (RB) components of the Modified Mayo) will be calculated from valid entries obtained prior to baseline endoscopy preparation (see Appendix 1). The baseline endoscopy component of the Mayo will use the endoscopic appearance of the mucosa at the screening endoscopy. For other efficacy, health outcome, and safety assessments, baseline is defined as the last non-missing assessment recorded on or prior to the date of the first study drug administration at Visit 2 (Week 0).

Baseline for safety analysis is described in the safety section.

Change from baseline will be calculated as the visit value of interest minus the baseline value. If a baseline value or the value at the visit is missing for a particular variable, then the change from baseline is defined as missing.

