	Weight Z-score and percentile by sex and age will be calculated using the CDC growth data shown at: https://www.cdc.gov/nccdphp/dnpao/growthcharts/resources/sas.htm This approach uses a Box-Cox	Weight Z-score Weight Percentile	Observed weight z-score and percentile by sex and age	Missing if weight at visit is missing.
	transformation to calculate the weight z-score and percentile of the normal distribution for the corresponding age and sex.			
	Weight Percentile Change from Baseline	Weight Percentile CFB	Change from Baseline is calculated as Present weight percentile – Baseline weight percentile	Missing if baseline weight or weight at visit is missing.
	Observed height velocity by gender and age group. Age groups for which	Height velocity	Observed height velocity by gender and age group will be calculated at baseline	Data will be missing if either present height or previous height

Measure	Description	Variable	Derivation / Comment	Definition of Missing
	this will be summarized are 2 to <8, 8 to <12, and 12 to <18.		according to the following formula: (Present Height [cm] - Previous Height [cm])/Interval (months) Between Measurements × 12	is missing.
Assessment of Puberty	Total testosterone levels will be collected from male patients ≥9 years of age. Estradiol levels will be collected from female patients ≥9 years of age, until the female begins menstruating. If the patient is 9 years of age and has already begun menstruation, estradiol levels will not be required.	Hormone level	Total testosterone levels for male patients ≥9 years of age and estradiol levels for female patients ≥9 years of age, until the female begins menstruating.	Missing if patients are less than 9 years old or if date of onset of menstruation for females if exists. Missing if missing.
EIMs	Extraintestinal manifestations (EIMs) are collected using the	Baseline EIMs	EIMs ongoing at first dose of study treatment.	No Imputation.

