	PUCAI clinical response	Proportion for each weight/treatment	mITT	Weeks 12 and 52
		dose group along with the 95%	mITT who achieve PUCAI	Week 52
		2-sided CI with NRI and as observed.	clinical response at Week 12	
	PUCAI CFB	Descriptive statistics and 95% CI for	mITT	Weeks 12, 24, 36, and 52
		mean with mBOCF and as observed.		

		Analysis Method	Population	
Measure	Variable	(Section 6.1.3)	(Section 6.1.1)	Time Point(s)
Height	Height Velocity	Descriptive statistics and 95% CI for	mITT, by gender and age	Weeks 12, 24, and 52
	II : 14 CED	mean.	group	W 1 12 24 152
	Height CFB	Descriptive statistics and 95% CI for mean.	mITT	Weeks 12, 24, and 52
	Height Percentiles CFB	Descriptive statistics and 95% CI for mean.	mITT	Weeks 12, 24, and 52
Weight	Weight CFB	Descriptive statistics and 95% CI for mean.	mITT	At each scheduled visit.
	Weight Percentiles CFB	Descriptive statistics and 95% CI for mean.	mITT	Weeks 12, 24, and 52
Occipital head circumference	Head circumference	Descriptive statistics and 95% CI for mean.	mITT only on those patients less than 3 years at baseline	At all applicable visits (Week 12 + Q12W)
Puberty Development	Testosterone CFB	Descriptive statistics and 95% CI for mean.	mITT – males who are 9 years or older	Weeks 12, 36, and 52
	Estradiol CFB	Descriptive statistics and 95% CI for mean.	mITT – females who are 9 years or older without the date of onset of menstruation.	Weeks 12, 36, and 52
Abdominal Pain NRS	Abdominal Pain NRS score CFB	Descriptive statistics and 95% CI for mean with mBOCF and as observed.	mITT, summarized by age group	Weeks 12 and 52
. The	CCI			Week 12 and 52
CCI			mITT	Weeks 12 and 52
Histopathology	Histologic Remission	Proportion for each weight/treatment dose group along with the 95% 2-sided CI with NRI and as observed.	mITT	Weeks 12 and 52
	Histologic Improvement	Proportion for each weight/treatment dose group along with the 95% 2-sided CI with NRI and as observed.	mITT	Weeks 12 and 52

		Analysis Method	Population	
Measure	Variable	(Section 6.1.3)	(Section 6.1.1)	Time Point(s)
	Histologic-Endoscopic	Proportion for each weight/treatment	mITT	Weeks 12 and 52
	Mucosal Improvement	dose group along with the 95%		
		2-sided CI with NRI and as observed.		
	Histologic-Endoscopic	Proportion for each weight/treatment	mITT	Weeks 12 and 52
	Mucosal Remission	dose group along with the 95%		
		2-sided CI with NRI and as observed.		

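### The SAP does not say when menarche status is judged for the estradiol analysis; read literally, girls who reach menarche on study lose estradiol values already collected

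*SAP*

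**What the plan says.** The secondary objective is the effect of mirikizumab on pubertal development, and its endpoint is broad: "Hormone levels and/or other related clinical measures will be evaluated" (SAP section 4.2).

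For girls, the SAP turns this into estradiol change from baseline at Weeks 12, 36 and 52:

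- **Collection** (Table AMBU.6.4): "Estradiol levels will be collected from female patients ≥9 years of age, until the female begins menstruating". The same entry adds: "If the patient is 9 years of age and has already begun menstruation, estradiol levels will not be required".
- **Missing-value rule** (Table AMBU.6.4): "Missing if patients are less than 9 years old or if date of onset of menstruation for females if exists".
- **Analysis population** (Table AMBU.6.5): the mITT population, restricted to "females who are 9 years or older without the date of onset of menstruation".
- **Change from baseline** (SAP section 6.1.2): if the baseline value or the visit value is missing, "then the change from baseline is defined as missing". The hormone rows of Table AMBU.6.5 name no imputation method.

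For boys, the testosterone row covers "males who are 9 years or older", with no restriction by maturation.

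Protocol section 9.1.6.3 states: "The date of onset of menstruation will also be collected". The rest of that section is redacted. Protocol section 9.4.3.2 aims hormone testing at patients not yet fully mature at Visit 1, which is a status at entry.

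**The concern.** Menarche can happen during the 52 weeks. A population defined by the absence of a menarche date, with no reference time, can therefore depend on something that happens after baseline and that is part of the outcome under study. A girl who reaches menarche late in the study acquires a date. On a literal reading she then no longer belongs to the population, and her hormone level counts as missing at every visit, including visits at which blood was drawn.

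Two things are at stake. First, values already collected from a child may be discarded, and the remaining girls would be selected on not having reached a pubertal milestone. If girls who reach menarche also tend to have larger estradiol changes, the mean understates progression. Second, the menarche date is used only to exclude patients or blank values. No visible row of Tables AMBU.6.5 or AMBU.6.6 reports how many girls reached menarche, so a reader could not tell who had left the later estradiol means.

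**Working it through.** The plan gives no figure for this analysis, so there is nothing to reproduce. The check compares the possible readings and then gives an illustration on stated assumptions.

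**Step 1: three readings of the rule.** Take a girl who is premenarchal at entry, has estradiol drawn at baseline, Week 12 and Week 36, and reaches menarche at Week 40.

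| Reading | Week 12 | Week 36 | Week 52 |
|---|---|---|---|
| (a) A date at any time removes her | lost | lost | lost |
| (b) Values drop out from menarche onward | kept | kept | not collected |
| (c) Only girls menstruating at baseline are removed | kept | kept | not collected |

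Reading (a) is the literal one: the date exists, so she is outside the Table AMBU.6.5 population and her hormone level is missing under Table AMBU.6.4. Reading (b) fits the collection rule. Reading (c) fits the Visit 1 wording in Protocol section 9.4.3.2. The readings differ over the visits before menarche. After menarche they agree: there is no value, so under section 6.1.2 there is no change from baseline.

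**Step 2: is the missing time reference deliberate?** Elsewhere the SAP states the time. Head circumference is limited by age at baseline (Table AMBU.6.5). Nocturnal stool, loose stool and extraintestinal manifestations are limited by status at baseline (Table AMBU.6.6). The estradiol row has no such anchor, so a programmer could build any of the three populations.

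**Step 3: how many girls (illustration).** Only the total of about 30 patients comes from the documents (SAP section 5.2). Every share below is an assumption.

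| | Low | Middle | High |
|---|---|---|---|
| Female | 40% | 50% | 60% |
| Aged 9 or older | 50% | 60% | 80% |
| Premenarchal at baseline | 30% | 50% | 70% |
| Reach menarche in 52 weeks | 10% | 20% | 40% |
| Girls aged 9 or older | 30 × 0.4 × 0.5 = 6.0 | 30 × 0.5 × 0.6 = 9.0 | 30 × 0.6 × 0.8 = 14.4 |
| Premenarchal at baseline | 6.0 × 0.3 = 1.8 | 9.0 × 0.5 = 4.5 | 14.4 × 0.7 = 10.1 |
| Reach menarche on study | 1.8 × 0.1 = 0.2 | 4.5 × 0.2 = 0.9 | 10.1 × 0.4 = 4.0 |
| Left under reading (a) | 1.6 | 3.6 | 6.0 |

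About 4 girls in each column are already postmenarchal at baseline (4.2, 4.5 and 4.3). Leaving them out is an ordinary restriction by entry status.

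**Step 4: shift in the mean (illustration).** Suppose a fraction p of the premenarchal girls is lost because they progressed furthest, and progression has correlation ρ with estradiol change. With both on a normal scale, the mean of those who remain shifts by

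shift = −ρ × φ(z) / (1 − p) SD, where z is the (1 − p) quantile and φ is the standard normal density.

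For p = 0.2, z = 0.842 and φ(z) = 0.280, so φ(z)/(1 − p) = 0.350.

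| p | ρ = 0 | ρ = 0.3 | ρ = 0.6 | ρ = 0.9 |
|---|---|---|---|---|
| 10% | 0 | −0.06 | −0.12 | −0.18 |
| 20% | 0 | −0.10 | −0.21 | −0.31 |
| 30% | 0 | −0.15 | −0.30 | −0.45 |
| 40% | 0 | −0.19 | −0.39 | −0.58 |

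Under reading (a), p is the share who ever acquire a date, and it applies at all three visits. Under (b) and (c), p is the share past menarche by the visit in question. The documents give neither p nor ρ.

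**The case against.** The strongest reply is that removing the whole patient is an inference. Table AMBU.6.4 says that estradiol is taken until menstruation begins, which suggests that values before menarche are meant to be used. Its missing-value column governs hormone values and can be read visit by visit, and the protocol defines the testing group at entry. This stands in part: reading (a) is one of three. But the SAP does not choose between them, so the ambiguity remains.

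A reader might go further and infer that the whole pubertal-development summary is confined to patients who did not progress. The documents do not support that. Testosterone in boys has no such filter, the endpoint allows other clinical measures, and girls whose puberty advances without menarche stay in. Nor would girls who reach menarche vanish from the report: they remain in the height and weight summaries on the mITT population.

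It is also fair to say that the bias is not demonstrated. Its direction depends on a positive correlation that the documents do not give, and at zero correlation the shift is zero.

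Finally, redefining the population recovers nothing after menarche, because that gap comes from data collection. This stands, and it is why a count of girls reaching menarche is needed as well. The absence of such a count can be asserted only for the visible text, since Protocol section 9.1.6.3 is largely redacted.

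**Conclusion.** The point holds as an unanchored definition with a possible loss of data. On the literal reading, estradiol values collected before menarche are discarded and the summary is conditioned on a pubertal event after baseline, which may understate progression. On every reading, girls who reach menarche leave the later means without any visible table showing it.

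The size cannot be determined from the documents. On the assumptions above, 0.2 to 4 girls are affected and roughly 2 to 6 remain under reading (a). The mean shifts by 0 to −0.58 SD, depending on a correlation that is itself assumed. The point is minor: it touches one descriptive secondary row for girls, with no treatment comparison planned. With so few girls, though, losing one or two can visibly change the summary.

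**What to change.** Three changes to the SAP:

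1. **Table AMBU.6.5, estradiol row:** define the population as mITT girls aged 9 or older who are premenarchal at baseline.
2. **Table AMBU.6.4, missing-value rule:** set estradiol to missing only from the menarche date onward, so that all earlier values are used.
3. **New display:** beside each estradiol summary (Weeks 12, 36 and 52), give the number and percentage of these girls who have reached menarche by that visit, from the date already collected.

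A footnote should say that values after menarche are not collected, so the Week 36 and Week 52 means describe girls still premenarchal at those visits.

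The cost is two edited table entries and one small extra table. No new data or assessments are needed.

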6.1.3. Analysis Methods

For assessments of the binary efficacy endpoints and binary health outcomes, proportions for each weight class/treatment group along with the 95% confidence intervals (CIs) using the Wilson Score method (Wilson 1927; Newcombe 1998) will be provided. Non-responder imputation method will be used to estimate the percentage of patients achieving response across post-baseline visits.

Assessments of the continuous endpoints, descriptive statistics (n, mean, standard deviation [SD], minimum, first quartile, median, third quartile, and maximum) will be provided for each specified visit. Where appropriate, the mean and mean change from baseline with corresponding 95% CIs will be presented at each specified visit.

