6.3.1. Non-Responder Imputation (NRI)

For analysis of categorical efficacy and health outcomes variables, missing data will be imputed using an NRI method. Patients will be considered non-responders for the NRI analysis if they do not meet the categorical efficacy criteria or have missing clinical efficacy data at a time point of interest.

The NRI method may be used when the estimand of interest uses the composite strategy (FDA 2021) for handling intercurrent events. In this strategy, patients with any intercurrent events that lead to the permanent discontinuation of assigned study treatment are defined to have failed treatment for all subsequent time points.

In addition, patients who were not adequately assessed to determine if they meet the clinical requirements for response at the time point of interest are also considered to have failed treatment.

For any interim analyses that occur, patients who, based on their treatment start date, would not have completed the visit corresponding to the selected endpoint at the time of the database lock will not be included in the analysis of that endpoint. Patients who have discontinued or otherwise have missing data and would have otherwise completed that visit at the time of database lock will be counted as non-responders for the interim analysis.

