Prior failured of a JAKg inhibitor	No	Ever, Never
Prior corticosteroid failured	No	Ever, Never
Prior immunomodulator	NI	·
failure ^{d, h}	No	Ever, Never
Baseline UC Therapies		
Baseline corticosteroid useh	No	Yes, No
Baseline prednisone equivalent dose	Yes	None
Budesonide MMX	No	Yes, No
Baseline immunomodulator use ^h	No	Yes, No
Baseline corticosteroid and immunomodulator useh	No	Corticosteroid only, Immunomodulator, Neither, Both
Baseline use of oral aminosalicilatesi	No	Yes, No
Baseline use of methotrexateh	No	Yes, No
Baseline use of thiopurineh	No	Yes, No
Baseline Disease Characteristics		
Duration of UCi	Yes	<1 year, ≥ 1 to <3 years, ≥ 3 year to <7 years, ≥ 7 years
Age at Diagnosis of UCk	Yes	$<6, \ge 6$ to <10 year, ≥ 10 to <17 years
Historical Disease Severity	No	Ever Severe, Never Severe
Baseline Disease Extent	No	Ulcerative proctitis (rectum), Left-sided (descending or sigmoid colon), Extensive (transverse colon), Pancolitis (cecum or ascending colon)
Baseline Fecal Calprotectin	Yes	≤250 μg/g, >250 μg/g
Baseline C-reactive Protein (CRP)	Yes	≤6 mg/L, >6 mg/L
Baseline Modified Mayo Score	Yes	Moderate (4-6), Severe (7-9)
Baseline Total Mayo Score	Yes	Moderate (6-9), Severe (10-12)
Baseline Partial Mayo Score	Yes	None
Baseline Endoscopic Mayo Subcore	No	Possible values of 4-point scale in Table AMBU.6.4
Baseline Stool Frequency Mayo Subscore	No	Possible values of 4-point scale in Table AMBU.6.4
Baseline Rectal Bleeding Mayo Subscore	No	Possible values of 4-point scale in Table AMBU.6.4
Baseline PGA Mayo Subscore	No	Possible values of 4-point scale in Table AMBU.6.4
Baseline PUCAI	No	Severe (65-85), Moderate (35-60), Mild (10-30), None (<10)
CCI		
Baseline Abdominal Pain NRS	Yes	<4,≥4
Baseline Patient's Global Rating of Severity (PGRS)	Yes	None
Baseline Nocturnal Stool	Yes	Yes (≥1), No (0)
Baseline Bristol Stool Scale	No	Not Loose Stool (1 – 3), Loose Stool (4-5)

Abbreviations: ATC = Anatomical Therapeutic Chemical; BMI = body mass index; DOB = date of birth; eCRF = electronic case report form; JAK = Janus kinase; NRS = numeric rating scale; PGA = Physician's Global Assessment; PUCAI = Pediatric Ulcerative Colitis Activity Index; TNF = tumor necrosis factor; UC = ulcerative colitis

- ^a Age in years will be calculated as length of the time interval from the DOB to the informed consent date.
- b Body mass index (BMI) will be calculated as: $BMI(kg/m^2) = Weight(kg)/(Height(m))^2$.

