	24 hours. Responses are graded on a 6-point scale in which a score of 0 indicates the patient has no symptoms (that is, "none") and a score of 5 indicates that the patient's symptom(s) are "very severe."			
Nocturnal Stool	The Nocturnal Stool instrument is a single item asking the patient to record the number of stools they had during the night (or day, for shift workers) causing them to wake from sleep.	Nocturnal Stool Score	Calculated by averaging data from all available of Mocturnal Stool for a 7 day period as described in Appendix 1.	Missing if fewer than 4 available measurements in the relevant 7 days.
Fatigue NRS	CCI	Fatigue NRS Score	Calculated by averaging data from all available diary entries of Fatigue NRS for a 7 day period as described in Appendix 1.	Missing if fewer than 4 available measurements in the relevant 7 days.
Bristol Stool Scale	The Bristol Stool Scale is a single item that provides a pictoral and verbal description of stool consistency and form ranging from Type 1 (Hard Lumps) to Type 5 (Watery/liquid). An additional option provided was "6. Did not poop."	Bristol Stool Scale score	Calculated by using the worst value (ie, largest number from 1 to 5) from all available diary entries of Bristol Stool Scale for a 7-day period as described in Appendix 1. Responses of "Did not poop," will be counted as missing for that day.	Missing if fewer than 4 available measurements in the relevant 7 days.
		Loose Stool	Bristol Stool Scale score of 4 or 5.	Bristol Stool Scale score is missing
PUCAI	The PUCAI (Turner et al. 2007) is a clinician-administered, 6-item questionnaire that measures: abdominal pain; RB; stool	PUCAI Score	All items are answered as an average over the 'past 2 days'. A total disease activity score is calculated from 0 to 85, with	Missing if any component is missing.

Measure	Description	Variable	Derivation / Comment	Definition of Missing
	consistency; number of stools;		Severe: 65-85	
	nocturnal stools; and activity level		Moderate: 35-60	
	(see Appendix 7 of the protocol).		Mild: 10-30, and	
			None: <10.	
			The clinician will record the patient or	
			caregiver/legal guardian responses for the	
			PUCAI electronically as source data in the	
			tablet device at appropriate visits.	
		PUCAI clinical	PUCAI clinical remission is defined as a	Missing if any component is
		remission	PUCAI score of <10 points	missing.
		PUCAI clinical	PUCAI clinical response is defined as a	Missing if any component is

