Abbreviations: CFB change from baseline; CI = confidence interval; mBOCF = modified baseline observation carried forward; mITT = modified intent-to-treat; MMS = Modified Mayo Score; NRI = non-responder imputation; NRS = Numerical Rating Scale; PUCAI = Pediatric Ulcerative Colitis Activity Index; Q12W = every 12 weeks.

 Table AMBU.6.6.
 Description of Exploratory Efficacy/Health Outcomes Analyses

Measure	Variable	Analysis Method (Section 6.1.3)	Population (Section 6.1.1)	Time Point(s)
Mayo Score and components	Change from baseline in SF, RB, and Total Symptomatic Score	Descriptive statistics and 95% CI for mean with mBOCF and as observed.	mITT	At each scheduled visit
	Change from baseline in ES	Descriptive statistics and 95% CI for mean with mBOCF and as observed.	mITT	Weeks 12 and 52
	Time to first symptomatic response	Descriptive statistics and 95% CI for mean.	mITT	During Induction Period
	Time to first symptomatic remission	Descriptive statistics and 95% CI for mean.	mITT	During Induction Period
	MMS Alternative Clinical Remission	Proportion for each weight/treatment dose group along with the 95% 2-sided CI with NRI and as observed.	mITT	Weeks 12 and 52
CRP	CRP CFB	Descriptive statistics and 95% CI for mean with mBOCF and as observed.	mITT	Week 12 Week 52
Fecal calprotectin	Fecal calprotectin CFB	Descriptive statistics and 95% CI for mean with mBOCF and as observed.	mITT	Week 12 Week 52
PGIC	Mean PGIC Score	Descriptive statistics and 95% CI for mean as observed.	mITT	Week 4, Week 8, Week 12, and Week 52
PGRS	PGRS Score CFB	Descriptive statistics and 95% CI for mean with mBOCF and as observed.	mITT	At each scheduled visit.
Nocturnal Stool	Nocturnal Stool Score CFB	Descriptive statistics and 95% CI for mean with mBOCF and as observed.	mITT - In patients with a nocturnal stool score ≥1 at baseline	At each scheduled visit.
CCI				At each scheduled visit.
Bristol Stool Scale	Loose stool	Proportion for each weight/treatment dose group along with the 95% 2-sided CI with NRI and as observed	mITT, in patients with loose stool at baseline	At each scheduled visit.

		Analysis Method	Population	
Measure	Variable	(Section 6.1.3)	(Section 6.1.1)	Time Point(s)
EIMs	Resolution of Baseline EIMs	Proportion for each weight/treatment dose group along with the 95% 2-sided CI with NRI and as	mITT – in patients with EIMs at baseline	Weeks 12 and 52
		observed.		

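### Non-responder imputation is attached to 'Loose stool', an unfavourable state, with no favourable responder variable defined; read literally, it codes missing patients as free of loose stool

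*SAP*

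**What the plan says.** In SAP Table AMBU.6.6 the Bristol Stool Scale row names the variable *Loose stool*. Its method is "Proportion for each weight/treatment dose group along with the 95% 2-sided CI with NRI and as observed", its analysis set is "mITT, in patients with loose stool at baseline", and it is reported at each scheduled visit.

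SAP Table AMBU.6.4 defines the variable as a "Bristol Stool Scale score of 4 or 5", on a scale that runs from hard lumps (1) to watery (5). The weekly score is the worst daily value. Days recorded as having no stool count as missing, and a week with fewer than 4 available days is missing. The complementary category, scores 1 to 3, appears only as a baseline descriptor in Table AMBU.6.3.

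SAP Section 6.3.1 gives the imputation rule: "Patients will be considered non-responders for the NRI analysis if they do not meet the categorical efficacy criteria or have missing clinical efficacy data". It also explains the purpose. Patients whose intercurrent event ends study treatment for good "are defined to have failed treatment for all subsequent time points", and patients not adequately assessed "are also considered to have failed treatment". Section 6.1.3 adds: "Non-responder imputation method will be used to estimate the percentage of patients achieving response across post-baseline visits".

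**The concern.** NRI is built for outcomes where meeting the criterion is good. Placing missing patients with those who do not meet it is then unfavourable to the drug. Here the named criterion is a symptom that the patient had at baseline and is hoped to lose. Not meeting it is the good result, so the same rule turns missing data into apparent benefit.

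Missing data are unlikely to be unrelated to outcome. Under Protocol Section 5.1, Week 12 nonresponders may discontinue, and patients on extended induction who have not improved enough by Week 24 stop study drug. Later visits will therefore tend to lack the patients who did worst. The issue also reaches patients still on treatment whose diary week has fewer than 4 usable days.

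At stake is whether two programmers, each following Section 6.3.1, would produce the same table. As written, they might not.

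**Working it through.** The SAP gives no expected rate or sample size for this endpoint, so there is no figure to reproduce. The check applies the stated rule to the stated variable.

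**Step 1: the two readings**

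| Text applied | Class of a missing patient | Coding of *Loose stool* |
|---|---|---|
| Section 6.3.1 rule, with score 4 or 5 as the criterion | Criterion not met | Not loose |
| Section 6.3.1 purpose (failed treatment) and Section 6.1.3 (achieving response) | Treatment failure | Still loose |

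**Step 2: size of the difference**

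Let n be the patients with loose stool at baseline, m those missing at the visit, and x those observed with loose stool.

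- Literal coding: A = x/n
- Missing as failure: B = (x + m)/n
- As observed: C = x/(n − m)

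Then B − A = m/n, whatever x is. Because n ≥ n − m, A ≤ C: the literal NRI rate can never exceed the as-observed rate, and for a fixed x/(n − m) it falls as m rises.

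**Step 3: illustration**

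The counts are assumptions: n = 25, x = 9, m = 7. Intervals use the Wilson score method named in Section 6.1.3, with z = 1.96:

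centre = (p + z²/2n)/(1 + z²/n); half-width = z·√(p(1 − p)/n + z²/4n²)/(1 + z²/n)

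| Coding | Rate with loose stool | Wilson 95% interval |
|---|---|---|
| Literal, missing = not loose | 9/25 = 36% | 20% to 55% |
| Missing = failure | 16/25 = 64% | 45% to 80% |
| As observed | 9/18 = 50% | 29% to 71% |

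The gap is 64 − 36 = 28 points, which is m/n = 7/25.

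**Step 4: range over missingness**

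Again with assumed counts: n = 20, half of the observed patients loose (as observed 50% throughout).

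| Missing | Literal | Missing = failure | Gap |
|---|---|---|---|
| 2 (10%) | 9/20 = 45% | 11/20 = 55% | 10 points |
| 4 (20%) | 8/20 = 40% | 12/20 = 60% | 20 points |
| 6 (30%) | 7/20 = 35% | 13/20 = 65% | 30 points |

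Results are reported by weight/dose group, and SAP Section 5.2 plans about 10 patients above 40 kg. If all 10 had loose stool at baseline, with 2 missing and 4 of 8 observed loose, the rates would be 4/10 = 40% and 6/10 = 60%.

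**The case against.** The strongest reply is that the SAP nowhere says dropouts are counted as free of loose stool. A reader might infer that from Table AMBU.6.6, but the documents do not support it as a stated rule. Section 6.3.1 labels the missing class non-responders and treatment failures, and Section 6.1.3 speaks of achieving response. Having loose stool is hardly an efficacy criterion, and restricting the set to patients loose at baseline fits an analysis of improvement. On that view a sensible programmer would count a missing patient as not improved. This stands: the anti-conservative coding is one of two readings. What remains is that the only variable defined is the unfavourable one, so the intended direction must be guessed.

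Two further inferences should also be resisted.

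- That every other NRI endpoint in Table AMBU.6.6 is conservative. One row is redacted, and the row for resolution of extraintestinal manifestations is unsettled: Table AMBU.6.4 specifies no imputation for it and Table AMBU.6.6 specifies NRI.
- That the bias equals the missing proportion. The quantity m/n is the gap between codings. It is bias only against a target that counts missing as failure. Against patients' true stool status, the error of the literal coding is the fraction both missing and truly loose, which is at most m/n.

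It is also fair to say that the consequences are limited. The as-observed result appears alongside, so a large discrepancy would show. No treatment comparison is planned (SAP Section 6.2), and the efficacy measures listed for the interim analysis in Section 6.16.2 are the modified Mayo and PUCAI measures, not the Bristol scale.

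**Conclusion.** The point holds as a defect of definition. NRI is attached to an unfavourable state without a favourable counterpart. The literal application codes any missing patient as not having loose stool, which conflicts with the failure intent of Section 6.3.1. The reported NRI rate could differ by m/n depending on who programs it: 10 to 30 points over assumed missingness of 10% to 30%, and 28 points in the 25-patient illustration. The counts are assumptions; the identity B − A = m/n is not.

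Severity is minor. The endpoint is exploratory and descriptive, the primary objective is pharmacokinetic, and no planned decision is tied to this row.

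**What to change.** In SAP Tables AMBU.6.4 and AMBU.6.6, replace *Loose stool* with *Resolution of loose stool*: a weekly worst Bristol score of 1 to 3 among patients with loose stool at baseline. State that a patient with a missing weekly score counts as not resolved under NRI. In the illustration, 18 − 9 = 9 observed patients have resolved, so the NRI result becomes 9/25 = 36% resolved, the complement of the 64% in the failure coding.

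If the sponsor prefers to keep the present variable, one sentence saying that missing is imputed as loose stool present would give the same information.

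The cost is one variable definition in two tables. No new data, procedures or protocol change are needed.
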